5.2. Randomization procedure

A blocked randomization will be performed. Each block will contain an equal number of allocations to KNO₃ followed by KCI versus KCI followed by KNO₃. The order of treatment sequences within each block will be randomized.

5.3. Intervention Phase 1

Subjects will be randomized to receive either active drug (KNO₃) or control (KCI) as the "first" drug for phase A. The initial dose will be one 6 mmol capsule administered twice daily, to be taken with meals. We will provide subjects with a 14-day supply of study medication to account for potential delays in receiving the 2nd batch of medication (i.e., after the 1-week call).

1-week call: Subjects will be called by telephone ~1 week later to assess if they are experiencing any side-effects. Subjects will receive reinforcement of the dietary restrictions imposed during the study. Subjects will be interrogated about headaches and dizziness. If these symptoms are not present, or are not worse compared to the subject's baseline, the drug dose will be up titrated to 18 mmol daily (One 6-mmol capsule taken 3 times per day). The presence of orthostatic symptoms (i.e. sustained lightheadedness upon standing) will prompt a visit to assess for orthostatic vital signs. The presence of symptomatic orthostatic hypotension (20 mmHg reduction in systolic blood pressure with associated symptoms such as dizziness) measured at this subsequent assessment visit will prompt exclusion of patients from the trial.

For subjects who have a serum K at the initial visit between 4.7 and 5.0 mEq/L in the presence of either: (a) potassium-sparing diuretic use, or (b) Estimated glomerular filtration rate of 30-39 mL/min/1.73m2, we will check a serum potassium 1 week after the implementation of the 18 mmol/d dose as a safety measure. A serum potassium > 5.5 mEq/L will prompt exclusion at this point.

At 3 weeks into each interventional phase, the Actigraph devices will be mailed to the subjects. The goal will be for the subjects to wear this device on their wrist during the final week of each interventional phase to look for differences with each therapy. The devices will be brought back by the subject at the endpoint visit.

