5.4. Washout period

Following the endpoint assessment, subjects will enter a 1-week \pm 3 day washout period during which they will not receive any study medications.

At 3 weeks into each interventional phase, the Actigraph device will be mailed to the subjects. The goal will be for the subjects to wear this devices on their wrist during the final week of each interventional phase to look for differences with each therapy. The device will be returned by the subject at the endpoint assessment.

5.5. Intervention Phase 2

Following the washout period, subjects will receive either active drug (KNO₃) or control (KCI) during phase 2 of the trial. Subjects will receive the intervention (KNO₃ or KCI) that was not administered to them in phase 1, such that each subject will receive both study interventions in this cross-over design. The ~1-week call and the ~4-week study visit will be repeated as above. We will provide subjects with a 14-day supply of study medication to account for potential delays in receipt of the 2nd batch of medication (i.e., after the 1-week call).

1-week call: Subjects will be called by telephone ~1 week later to assess if they are experiencingside-effects. Subjects will receive reinforcement of the dietary restrictions imposed during the study. Subjects will be asked about headaches and dizziness. If these symptoms are not present, or are not different than the subject's baseline, the drug dose will be up-titrated to 18 mmol daily (One 6-mmol capsule taken 3 times per day). The presence of orthostatic symptoms will prompt a visit to assess for orthostatic vital signs. The presence of symptomatic orthostatic hypotension (20 mmHg reduction in systolic blood pressure with associated symptoms such as dizziness) at the follow up visit will prompt exclusion of patients from the trial.

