5.7. Subject withdrawal / Early termination

Subjects may voluntarily withdraw from the study at any time and for any reason, or this may be at the investigator's discretion. The investigator may withdraw a patient from the study due to protocol non-compliance, incorrect enrollment or randomization, or for any other reasons related to subject safety. The reason for study discontinuation will be recorded on the source documents and all such subjects will be asked to complete an early termination visit.

During this visit, we will document: (1) vital signs; (2) compliance with the medications (3) Adverse effects. (4) Specific reason for withdrawal.

Subject Early Termination Visit Procedures

- Vital Signs and Physical Exam
- Medication adherence log
- Safety Labs
- Adverse event assessment
- Documentation of reason for withdrawal

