8.2. Quality of life

Quality of life will be assessed with the Kansas City Cardiomyopathy Questionnaire (KCCQ).⁽⁸⁶⁾ We will administer the KCCQ to subjects prior to randomization and at the end of each intervention phase (6-week time point in both phases). This is a validated 23-item questionnaire that assess physical function, symptoms, social function, self-efficacy and knowledge, and quality of life. It has been used extensively in heart failure studies (http://cvoutcomes.org/pages/3214)

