9.4. Data Management

The data for this trial will be collected in ad hoc source documents by the research staff during each study visit, using trial-specific and visit-specific data collection forms. All source documents collected in this trial will be housed inside of a locked cabinet in the offices of the research staff. Data capture and storage will be accomplished within the framework of the Research Electronic Data Capture (REDCap) project. REDCap is a secure, web-based application designed exclusively to support data capture for research studies. It provides an intuitive interface for data entry with data validation, audit trails for tracking data manipulation and export procedures, automated export procedures for seamless data downloads to common statistical packages, including SAS, and procedures for importing data from external sources. As of March 2015, REDCap was in production use or prototype build-status for more than 99,000 studies spanning numerous research focus areas across a consortium of 940 active institutional partners, including the University of Pennsylvania. Once the REDCap database is launched into production mode, the study coordinators will be responsible for transmitting the participant coded electronic data using standardized data collection instruments to the database manager who will check the data

for accuracy and completeness and follow-up with the research assistants as needed. The research coordinators will perform manual data entry from source documents and self-administered participant questionnaires (such as quality of life questionnaires).

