The intent-to-treat principle of including all randomized participants in the outcome models will be followed. SAS software procedures will be used for creating and analyzing multiple imputed data sets for incomplete multivariate data. Instead of filling in a single value for each missing value, Rubin's⁽¹¹⁷⁾ multiple imputation procedure replaces each missing value with a set of plausible values that represent the uncertainty about the correct value to impute. These multiple imputed data sets are then analyzed using standard procedures for complete data and combining the results from this analysis. Assuming monotone missing data patterns emerge, either a parametric regression method that assumes multivariate normality or a nonparametric method that uses propensity scores will be implemented, depending upon distributional patterns.

Analytic methods described above will take advantage of all available data. The possibility of systematic bias in the outcomes for those who withdraw exists. Baseline characteristics will be compared among subjects with and without complete follow-up, recognizing that statistical power associated with finding true statistical differences may be limited. To assess potential biases, a comparison of withdrawal rates and or/time to withdrawal will be included. If the number of subjects lost to follow-up is small and the missing observations can be documented as being MAR or MCAR, then the primary hypotheses will be tested using the complete observed data. If missing observations cannot be assumed to be MAR or MCAR, more complex approaches will be considered. Sensitivity analyses for these models will be performed should they be implemented.⁽¹¹⁸⁾

Our secondary aims involve exploratory analyses investigating mechanisms of action. In addition to assessing the effect of our randomized intervention on each mechanistic endpoint, exploratory structural equation modeling will be used to evaluate associations between outcomes and biologic mechanistic pathways. The modeling will be carried out in three sequential steps: (1) exploratory factor analysis, (2) confirmatory factor analysis, and (3) structural equation modeling. The exploratory factor analysis will be based on principal axis factoring to decrease the number of

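### A subject removed mid-phase for symptomatic orthostatic hypotension has no KCCQ for that phase, so the all-randomized KCCQ analysis rests there on imputation or model assumptions

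*Combined protocol and SAP*

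**What the plan says.** - **Removal.** In phase 1 (section 5.3), orthostatic symptoms lead to an extra visit, and a symptomatic 20 mmHg systolic fall "measured at this subsequent assessment visit will prompt exclusion of patients from the trial". Section 5.5 has the same rule for phase 2: such a fall "at the follow up visit will prompt exclusion of patients from the trial". Section 11.3.3 repeats it for any point in the trial. Removal is from the trial, not only from the drug.
- **After removal.** Section 5.7 covers withdrawals by the subject and by the investigator, including those for safety, and says "all such subjects will be asked to complete an early termination visit". For that visit it says: "During this visit, we will document: (1) vital signs; (2) compliance with the medications (3) Adverse effects. (4) Specific reason for withdrawal". The procedure list that follows adds a physical examination and safety laboratory tests. Neither list has KCCQ.
- **KCCQ timing.** Section 8.2: "We will administer the KCCQ to subjects prior to randomization and at the end of each intervention phase". Appendix 1 agrees and has no early-termination column. Section 9.4 says that data are collected "using trial-specific and visit-specific data collection forms".
- **Analysis.** Section 10.2 names peak VO2 and KCCQ as co-primary. It says that the mixed models include data from dropouts, and: "The intent-to-treat principle of including all randomized participants in the outcome models will be followed". It then specifies multiple imputation. It also promises an effort to obtain final assessments, worded for participants who choose to stop.
- **Endpoint status.** Section 1 names total work and peak VO2 as co-primary instead. Section 2 lists quality of life as a secondary aim but KCCQ as a primary endpoint. This point follows section 10.2.

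**The concern.** The analysis section promises an all-randomized KCCQ comparison, but the visit schedule does not collect KCCQ from one group: those taken out mid-phase because of a blood-pressure effect that KNO3 might cause. Section 7.2 lists such falls as a potential, though unexpected, effect of KNO3. A KNO3-first subject removed in phase 1 has only a baseline KCCQ. A KCl-first subject removed in phase 2 has a KCl value but none on KNO3.

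If such removals fall mainly on KNO3 and those subjects feel worse on it, the phase-end comparison leans towards subjects who tolerated the drug while being reported as intent-to-treat. A questionnaire that was not given at that visit cannot be obtained later.

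**Working it through.** **1. Is there another route to the value?** KCCQ is scheduled at baseline and at the two phase-end visits only (section 8.2, Appendix 1). A subject removed mid-phase does not reach that phase's end visit. The early-termination lists omit KCCQ. The promise of final assessments in section 10.2 speaks of subjects who choose to stop, and no listed procedure carries it out. So no planned step collects it.

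**2. The plan's own figure.** Section 10.1: 22 enrolled, 90% retention, two-sided 0.05, 80% power at a standardized effect of 0.66. With 22 × 0.90 = 19.8, rounded to 20 pairs, a paired t-test (noncentral t) has 79.95% power at 0.66. The figure reproduces.

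**3. Implied KCCQ spread.** Section 10.1 gives a detectable KCCQ change of 4.6 points and no SD. Implied SD of the paired difference = 4.6 / 0.66 = 7.0 points (an inference). SE with 20 pairs = 7.0 / √20 = 1.57.

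**4. Bias formula.** Let k subjects be removed on KNO3, R be the mean effect (KNO3 minus KCl) in retained subjects and D the effect in removed subjects. The all-randomized effect is [(22 − k)R + kD] / 22, so

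overstatement = R − all-randomized effect = (k/22)(R − D).

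Section 10.2 expects about 10% not to complete for any reason, about 2 of 22, so k = 1 or 2. D is not in the documents. I assume −5 or −10 points, with 0 as a milder case.

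**5. Results.** If the all-randomized effect is 0 and D = −g, then R = kg/(22 − k). The last column is the chance of a significant result favouring KNO3 (nominal 2.5%), from the noncentral t with 22 − k pairs and SD 7.0.

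| k | D | R when true effect is 0 | Overstatement when R = 4.6 | False benefit |
|---|---|---|---|---|
| 1 | −5 | 5/21 = 0.24 | 9.6/22 = 0.44 | 3.5% |
| 1 | −10 | 10/21 = 0.48 | 14.6/22 = 0.66 | 4.8% |
| 2 | −5 | 10/20 = 0.50 | 2 × 9.6/22 = 0.87 | 4.9% |
| 2 | −10 | 20/20 = 1.00 | 2 × 14.6/22 = 1.33 | 8.8% |

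With D = 0 the overstatement is 0 when R = 0. When R = 4.6 it is 4.6/22 = 0.21 (k = 1) or 9.2/22 = 0.42 (k = 2). With k = 0 it is always 0.

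**6. Does imputation close the gap, and would an early KCCQ help?** I simulated two removals on KNO3, one per sequence, with a true all-randomized effect of 0. Assumptions: between-subject SD 20, within-subject SD 6.97/√2, baseline and period in the model, variance components known. Results for D = −5 and −10:

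- Phase-end mixed model: bias of 0.50 and 1.02 points.
- Regression multiple imputation from retained subjects: 0.55 and 0.91.
- Early-termination KCCQ entered as that phase's value: 0.12 and 0.26.
- Early value, but 5 points lower still because of passing symptoms: −0.23 and −0.09.

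If removed subjects respond like the others (true effect 3) and only the early value dips by 5 points, entering it gives 2.69, about 0.3 too low.

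**The case against.** The plan is not blind to dropout. Section 10.2 recognises possible bias from withdrawals, promises a comparison of withdrawal rates or times, will examine the missingness mechanism, and allows more complex methods with sensitivity analyses. Such analyses can shift unobserved values by assumed amounts without new data. The event also looks unlikely: section 11.3.3 excludes subjects with a fall above 20 mmHg at screening and reports no hypotension in the earlier studies. The early value may come at about one week, on 12 mmol/d, in a symptomatic subject, so it is not the four-week endpoint. All of this stands. It limits the size of the problem, but it does not supply the missing observation.

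A reader might infer four stronger points that the documents do not support:

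- **That the model has nothing to include for these subjects.** Every subject has a baseline KCCQ, one removed in phase 2 keeps the phase 1 value, and multiple imputation is specified.
- **That no subject with a confirmed fall has a KCCQ.** Orthostatic pressure and KCCQ are both taken at the phase-end visits (sections 5.3 and 5.5), so a fall first found there has its KCCQ for that phase. Subjects with headache or with unconfirmed orthostatic symptoms are not removed by the rule, so imputation is not confined to symptom-free records.
- **That potassium removals add to the bias.** Section 5.3 also says "A serum potassium > 5.5 mEq/L will prompt exclusion at this point" for a tested subset, but the control is KCl at the same dose (section 4.4). These removals have no evident reason to favour either treatment.
- **That no sensitivity analysis would be possible.** Shift-based analyses remain available. They would rest on assumption where one observation could have been had.

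**Conclusion.** The gap is real and narrow. For a subject removed mid-phase after a confirmed symptomatic fall, that phase has no observed KCCQ. The all-randomized analysis then rests on imputation or model assumptions informed mainly by subjects who tolerated treatment.

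The documents do not show that the KCCQ result will be overstated. The illustrative bias of about 0.2 to 1.3 points needs one or two removals, all on KNO3, and an assumed deficit of 5 or 10 points. The top of the range needs both expected non-completers to be such cases, each 10 points worse, the size that section 10.1 treats as clinically significant. If KNO3 has no effect in removed subjects, the overstatement is 0 to 0.4 points. All these figures are below the SE of 1.57.

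This is a cheap improvement, not a flaw that undermines the trial. Peak VO2 and total work have the same gap. The safety monitoring plan (Appendix 3) is not in the supplied text and could not be checked.

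**What to change.** 1. **Section 5.7 and Appendix 1:** add KCCQ to the early-termination procedures for all withdrawn subjects, whatever the reason, and record the current dose and days since the last dose.
2. **Section 10.2:** keep the planned phase-end model as the main KCCQ analysis. Pre-specify one sensitivity analysis that enters the early-termination KCCQ as that phase's value, reported beside the main estimate with its 95% confidence interval.

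The cost is one 23-item questionnaire at an existing visit, for about 2 subjects, and a few sentences of text. The early value may reflect a short exposure, the 12 mmol/d dose and passing symptoms, so it belongs only in a sensitivity analysis. It does not complete the pair for a subject removed in phase 1, and it does not restore peak VO2 or total work. No exercise test is proposed at that visit.

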4. STUDY DESIGN AND POPULATION

4.1. Overview of study design

In this phase IIb, double-blind, cross-over trial, we will assign 22 subjects who are post-AVR for severe AS to: (A) Potassium nitrate administered by mouth at a dose of 6 mEq three times daily for 4 ± 1 weeks, or (B) Potassium chloride (KCl) at identical doses. The order of the interventions (AB-BA design) will be randomized, with a 1-week \pm 3 day washout period separating each intervention. A crossover design will enable each subject to receive both treatments, reducing inter-individual variability and maximizing our power to detect effects of potassium nitrate vs. control (KCl). The active drug (KNO₃-) and control (KCl) will be prepared at the Investigational Drug Pharmacy at the University of Pennsylvania and dispensed by an investigational drug pharmacist, blinded to both the subjects and the investigators.

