10. STATISTICAL CONSIDERATIONS

10.1. Power calculations

We will randomize 22 subjects to one of 2 sequences (i), each of which consists of 2 periods (AB/BA design). We now have pilot data regarding the distribution of the changes in peak VO₂ (the primary endpoint of the study) as well as various secondary endpoints, among patients with HFpEF. We considered an increase in peak VO₂ of ~0.6 ml/kg/min to be the minimum clinically-significant change. This was based on the fact that even "modest" changes of comparable magnitude in peak VO₂ have been associated with improved outcomes.⁽¹¹⁰⁾ The standard deviation of the change in peak VO₂ in our pilot trial was 1.23 ml/kg/min. Therefore, the standardized effect size is 0.49 or greater. Assuming a 90% retention rate, enrolling 22 subjects in this cross-over trial will have 80% power to detect an effect size as low as 0.66 in the intervention-induced change of our study endpoints, with a two-sided α =0.05.

Based on the distribution of the changes in study endpoints from repeated measurements of the Kansas City Cardiomyopathy Questionnaire in AS patients, we estimated that this trial study is powered (80%) to detect the following changes in other endpoints: 4.6 points for the Kansas City Cardiomyopathy Questionnaire, 8.2% for exercise vasodilatory reserve, 19% for cardiac output reserve and 4.2% change in reflection magnitude. We note that these differences are well below what is considered a clinically significant change in KCCQ (10 points or more, http://cvoutcomes.org/pages/3217) or the effect size that has been observed for these endpoints in our pilot trial.⁽⁸⁵⁾ Therefore, we are confident that we will achieve adequate power not only for our clinical endpoints, but also for our physiologic measures. PASS11⁽¹¹¹⁾ was used to perform power analyses.

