described above using parametric or non-parametric one-way ANOVA models, depending upon whether or not normality appears to be in question. Levine's tests will be used to assess homogeneity of variance. Additionally, the intervention groups will be compared within period according to categorical covariates using Fisher's Exact tests. Significant differences between groups on these variables will result in their use as control variables in the modeling of outcome. Separate models will be generated for each of the two outcome measures, with each outcome measure regressed on intervention group assignment, along with baseline outcome and any other covariates deemed prognostic in preliminary analyses. The linear mixed-effects models will incorporate adjustments for any period effect and include data from dropouts.⁽¹¹³⁻¹¹⁵⁾ The model will include subject-specific intercepts as random effects, and assumes independent and identically distributed random errors within subject. Restricted maximum likelihood estimation will be used, and an appropriate covariance matrix will be specified. Model assumptions will be examined (e.g., QQ plots to assess normally distributed residuals for valid Wald tests). We will make every possible effort to minimize missing data and ensure final assessments for participants opting to discontinue study participation. Missing data, however, is an inevitable problem in a longitudinal study. The mechanism for missingness-missing completely at random (MCAR), missing at random (MAR), nonignorable or not missing at random (NMAR)-will be evaluated prior to implementing methodology intended to minimize bias from missing data.⁽¹¹⁶⁾ We anticipate that ~10% of randomized subjects will not complete the study.

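### Section 10.2 permits propensity-score imputation, which weakens the crossover pairing for imputed subjects and can cost power if that imputed result is used and the within-subject correlation is high

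*Combined protocol and SAP*

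**What the plan says.** Section 4.1 justifies the design by its pairing: "A crossover design will enable each subject to receive both treatments, reducing inter-individual variability and maximizing our power". Section 10.1 sets the size ("We will randomize 22 subjects to one of 2 sequences") and the power claim: "Assuming a 90% retention rate", "enrolling 22 subjects in this cross-over trial will have 80% power to detect an effect size as low as 0.66", "with a two-sided α =0.05". The variability input is "The standard deviation of the change in peak VO₂ in our pilot trial was 1.23 ml/kg/min", from patients with HFpEF.

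Section 10.2 expects some loss: "We anticipate that ~10% of randomized subjects will not complete the study". It then describes several routes:

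- A REML linear mixed model with period, sequence and a random subject effect, which is to include dropouts' data.
- Multiple imputation under the intent-to-treat principle. If the missing-data pattern is monotone, "either a parametric regression method that assumes multivariate normality or a nonparametric method that uses propensity scores will be implemented"; distribution shape decides which.
- A test of the primary hypotheses on the complete observed data, if few subjects are lost and the missingness can be documented as MAR or MCAR.

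The section does not say which variables enter the propensity score, whether a subject's other-period outcome must be used, or which route gives the primary result.

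**The concern.** Propensity-score imputation models the probability that a value is missing. It groups subjects by that probability and draws the missing value from observed subjects in the same group. Nothing in it ties the imputed period-2 value to that subject's own period-1 value, except indirectly when the period-1 value happens to drive the score. The imputed KNO3-minus-KCl difference can then carry between-subject spread that the crossover was chosen to remove. With about 2 non-completers, the score is also fitted on about 2 events.

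Dropout after period 1 is monotone, so that condition is easily met. Distribution shape alone then selects the method, although shape says nothing about whether the pairing is preserved. What is at stake is precision and power in any result that uses this imputation.

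**Working it through.** **Inputs.** From section 10.1: 22 randomized, 90% retention, SD of change 1.23, effect size 0.66, two-sided alpha 0.05. From section 10.2: about 10% non-completion, so about 2 of 22. Assumed, because the documents do not give it: within-subject correlation ρ between the two period values, 0.3 to 0.95.

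**The plan's own figure.** 22 × 0.9 = 19.8, about 20 pairs. A paired t-test with noncentrality 0.66 × √20 = 2.95 on 19 df has power 79.95%. The stated 80% reproduces.

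**What ρ means here.** With the SD of change fixed, the cross-sectional SD is 1.23/√(2(1−ρ)). At ρ = 0.5 this is 1.23 ml/kg/min; at 0.8 it is 1.94; at 0.9, 2.75; at 0.95, 3.89.

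**Closed form.** Suppose m subjects lack period 2, c = 22 − m are complete, and donors are drawn without regard to the subject's own period-1 value. The sampling variance relative to complete pairs is

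[1/c + 1/22 − 2ρ/22] / [2(1−ρ)/c].

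For c = 20 and ρ = 0.8: (0.0500 + 0.0455 − 0.0727)/0.0200 = 1.14. The ratio is 0.97 at ρ = 0.3, 1.00 at 0.5, 1.06 at 0.7, 1.36 at 0.9 and 1.82 at 0.95. Break-even is ρ = 0.5 for any m.

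**Simulation.** AB/BA trial, true effect 0.66 × 1.23 = 0.812, 2 of 22 missing period 2 completely at random, normal outcomes, five propensity groups with approximate Bayesian bootstrap of donors, 20 imputations, Rubin's rules. In the last column the lower figure has two unrelated covariates in the score; the upper has only the period-1 value and sequence.

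| ρ | Complete pairs, power | Propensity imputation, power |
|---|---|---|
| 0.3-0.5 | about 79-80% | about 77-78% |
| 0.7 | 80% | 72-75% |
| 0.8 | 79% | 69-74% |
| 0.9 | 81% | 58-69% |
| 0.95 | 80% | 43-60% |

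A separate run with three unrelated covariates agrees. Mean SE was 0.287, 0.303, 0.345 and 0.420 at ρ = 0.7, 0.8, 0.9 and 0.95, with power 72%, 70%, 56% and 42%, against an SE of 0.271-0.272 for complete pairs.

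Part of the loss is real sampling variation and part is an overstated Rubin variance. At ρ = 0.9 in that run the empirical SE was 0.309 and the mean reported SE 0.345. Coverage of the 95% intervals stayed at or above about 95%. The mean estimate was about 0.78-0.79 against 0.81.

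**Alternatives on the same footing.**

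- Regression imputation on the subject's own period-1 value and sequence: SE 0.276 and power 80% at ρ = 0.8 (complete pairs 0.271 and 82% in that run); 0.277 and 78% at ρ = 0.9 (0.271 and 79%).
- Mixed model on all available data, no imputation (GLS variance): SE 0.2717 to 0.2747 for ρ from 0.5 to 0.95, against √(1.23²/20) = 0.2750 for complete pairs. It is never worse.

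**The case against.** The strongest reply is that the plan need not rely on this imputation. The simulated case, two subjects missing completely at random, is the case that section 10.2 would send to a test on the complete observed data. The section also already plans a mixed model that keeps dropouts' data. Both preserve the design power. This stands. A reader might infer that the stated 80% power will not be delivered in the intent-to-treat analysis. The documents do not support that, because they leave open which route is used.

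The size depends on two things the plan does not state: the correlation and the contents of the score. At a correlation of 0.5 or below there is essentially no loss, and a score limited to the period-1 value and sequence loses less than one with unrelated covariates. It would therefore also be too strong to infer that propensity imputation is always less precise than dropping incomplete pairs, or that it destroys the pairing. About 20 of 22 pairs are untouched.

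The trigger is uncertain too. For non-normal outcomes section 10.2 also offers transformations and non-parametric methods, and nothing in the documents shows that KCCQ or total work will be non-normal. The figures above are for a normally distributed peak VO2; no non-normal outcome was simulated.

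Finally, not every dropout will miss only period 2. Section 5.3 allows exclusion after the one-week call, and Appendix 1 shows no baseline exercise test. Someone who leaves that early has no own peak VO2 value and adds no within-subject information under either imputation method.

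None of this gives a reason to keep the option. At moderate to high correlation it does worse than methods already in the section, and distribution shape is the wrong criterion for choosing it.

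**Conclusion.** The point holds as a conditional one. Section 10.2 names an imputation method that is poorly suited to a crossover and lets distribution shape select it. If its result were used with 2 of 22 missing period 2, the power loss would be negligible at a within-subject correlation of 0.3-0.5, roughly 5 to 10 points at 0.7-0.8, and about 10 to 37 points at 0.9-0.95. The correlation is assumed throughout, and the SD of 1.23 comes from HFpEF patients rather than this population. The harm is lost precision with slight attenuation; there is no sign of excess false positives. The wording should be changed, but this is not evidence that the trial's primary result will be invalid or underpowered.

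**What to change.** In section 10.2:

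1. Delete the propensity-score option.
2. Name the REML mixed model already planned (treatment, period, sequence, random subject), fitted to all observed data, as the primary analysis.
3. If multiple imputation is kept as a sensitivity analysis, use regression imputation or, for non-normal outcomes, predictive mean matching. In either case the imputation model should contain the subject's own other-period value of that outcome, sequence and period.
4. State that subjects with no exercise test contribute no within-subject information on peak VO2 and that imputation does not supply it.

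The cost is a sentence or two of text and no extra data. The downside is slightly less flexibility for non-normal outcomes, and predictive mean matching is coarse with about 20 donors.
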